4.8.7. Concomitant Medications

Prior and Concomitant medications will be coded using the WHO Drug dictionary. Frequencies and percentages will be presented for each treatment group and overall by Anatomic Therapeutic Class (ATC) and preferred name. Vitamin D and Calcium supplementation as collected in the eCRF at each visit will be summarized as well.

The use of concomitant medications will be included in a by-subject data listing.

Prior medications are those the subject used prior to the first day of treatment.

All medications administered between the date of the first dose of study drug and the date of the last dose of study drug, inclusive, (i.e., all medications starting or ongoing during the time interval) are concomitant. A medication taken prior to Study Day 1 and continuing post Study Day 1 will be considered both prior and concomitant.

Prior interventional surgeries/procedures for endometriosis/endometriosis symptoms will also be summarized.

4.8.8. Transvaginal Ultrasound (TVUS)

TVUS will be performed at Screening, Month 3, Month 6, Month 3 and Month 6 of the Follow-up period.

Actual values and changes from baseline will be summarized by treatment group and overall for uterus length, width, and depth in mm and corresponding uterine volume in cm3, as well as endometrium thickness in mm.

The number and percentage of subjects with any ovarian endometrioma with a diameter of 7 cm or greater, and presence of any uterus, left ovary or right ovary abnormality over time will be presented by treatment group and overall.

Sponsor:	ObsEva		
Protocol:	18-OBE2109-003		
Document Version No.:	V5.0	Document Date:	13-JUN-2022

4.8.9. **Other Examinations**

At least two endometrial biopsies for histological assessment were obtained for each subject:

- One at screening, unless an endometrium biopsy was performed within the past 6 months of the screening visit, which shows no atypical hyperplasia or adenocarcinoma and for which slides are available for current study assessment through retrospective central laboratory reading.
- One at Month 6 if the endometrium thickness via TVUS is > 5 mm
- One at Month 1 FU, 2 FU, 3 FU, 4 FU, 5 FU or 6 FU if not obtained at Month 6 or if the preceding biopsy diagnosis is different than "benign endometrium"

A summary at each time point will be performed (number and percentage of subjects with normal, abnormal, not assessable).

Biopsy diagnosis will be summarized by classification and primary diagnosis at each visit. Subjects will be counted only once per classification and diagnosis. A subject can be counted in several diagnoses.

Possible classifications and diagnoses are:

- Benign Endometrium without Hyperplasia or Atypia: Proliferative, Atrophic, Metaplastic Changes, Secretory, Indeterminate, Inactive, Polyp, Endometritis, Menstrual phase, Other
- Hyperplasia: Simple with Atypia, Simple without Atypia, Complex with Atypia, Complex without Atypia
- Malignant Endometrial Neoplasm: Carcinoma, Sarcoma, Other Malignant, Not applicable.

If any diagnosis does not correspond to any on the list, the diagnosis will be coded as: Other Malignant if classification is Malignant Endometrial Neoplasm, and Other for any other classification.

For biopsies with reported primary diagnosis "Hyperplasia" or "Malignant Endometrial Neoplasm" at other visits than screening, a second read of the biopsy was to be performed. If the diagnosis of the two reads was different, then the sample was to be re-read a 3rd time. In case of multiple readings, the following rules will be applied for the statistical analysis:

- If 2 readings out of 3 lead to the same diagnosis, one of these 2 records will be selected.
- Otherwise, the record corresponding to the most severe diagnosis should be selected considering the following order, from less severe to more severe: simple without Atypia hyperplasia < complex without Atypia hyperplasia < simple with atypia hyperplasia < complex with Atypia hyperplasia < endometrial malignant neoplasm < other malignant neoplasm.

In addition, in order to perform a quality check of the readings, 15% of biopsies were sent blinded for a second read when the primary diagnosis was "Benign Endometrium". In case of multiple readings when the primary diagnosis from the first read is "Benign Endometrium", this first read will be used for the analysis.

Sponsor:	ObsEva		
Protocol:	18-OBE2109-003		
Document Version No.:	V5.0	Document Date:	13-JUN-2022

Endometrial biopsy results will be reported in listings.

Due to the war situation in Ukraine, some biopsy samples may have been collected and analyzed by local laboratories. Those assessments will be flagged in the listings, for the Follow-up period only, as the main treatment period was completed before the start of the war. Information about local biopsy assessment is reported in Data Management Close queries file. This file will be provided by data management department and reviewed by Sponsor. Biopsy assessments performed locally can be identified in the queries list from Endometrial Biopsy page, by subject and visit and by word search, with answer to query containing the word "local".

Gynecological Examination is assessed at Screening, Month 3, Month 6 and Month 3 of Follow-Up period.

Breast examination (by palpation) will be performed at the Screening, Month 6 and Month 3 FU visits.

A summary at each time point will be performed (number and percentage of subjects with normal, abnormal, abnormal significant) for Gynecological and Breast Examinations. Results will also be reported in listings.

PAP Smear is collected at Screening. A listing of abnormality information and a listing of diagnosis results will be provided, including possible unscheduled assessments.

4.8.10. Columbia-Suicide Severity Rating Scale (C-SSRS)

The C-SSRS questionnaire prospectively assess the occurrence of treatment-emergent suicidal ideation and behavior.

Subjects will complete:

- either the "Baseline" C-SSRS version, capturing lifetime history of suicidal ideation and behavior, for subjects under screening at the time of/after protocol amendment 3 implementation,

- or the "already enrolled subjects" C-SSRS version, for subjects already randomized at the time of protocol amendment 3 implementation, and who are providing answers to the C-SSRS for the first time during the study

- the "since last study visit" C-SSRS version, dedicated to subjects for whom the C-SSRS was completed at the previous study visit, for use at all remaining study visits.

The "Baseline" C-SSRS version is to be completed during Screening, or at Day 1 if not done during Screening.

The following C-SSRS data will be summarized by time point (baseline "Lifetime" or Prior to Study Entry, "Since Study Start" and each post-baseline time point):

- Incidence of the following suicidal ideation:
 - Wish to be dead.

Sponsor:	ObsEva		
Protocol:	18-OBE2109-003		
Document Version No.:	V5.0	Document Date:	13-JUN-2022

- Non-specific active suicidal thoughts.
- Active suicidal ideation with any methods (not plan) without intent to act.
- Active suicidal ideation with some intent to act, without specific plan.
- Active suicidal ideation with specific plan and intent.
- Incidence of the following suicidal behavior:
 - Actual attempt.
 - Interrupted attempt.
 - Aborted attempt.
 - Preparatory acts or behavior.
 - Completed suicide (Actual attempt leading to death).

The number of subjects with any suicidal ideation, any suicidal behavior, and any suicidal ideation or behavior will be summarized at each time point.

The number of subjects experiencing the following, at any time post-baseline, will also be summarized

- Suicidal ideation or behavior
- Emergence of suicidal ideation.
- Worsening of suicidal ideation.
- Emergence of suicidal behavior.

Emergence of suicidal ideation/behavior is defined as having no suicidal ideation/behavior at baseline and having reported any type of suicidal ideation/behavior at any time post-baseline (including "Since Study Start" answers). Worsening of suicidal ideation is defined to occur when the most severe suicidal ideation rating since study start at any time post-baseline is more severe than its rating at baseline. The Suicidal ideation rating is defined as the following, as recommended in the C-SSRS scoring and analysis guide in https://cssrs.columbia.edu/wp-content/uploads/ScoringandDataAnalysisGuide-for-Clinical-Trials-1.pdf:

Maximal suicidal ideation category during the period (baseline, post-baseline up to Month 6, FU period) where categories range from 0 to 5:

- 0. No ideation
- 1. Wish to be dead
- 2. Non-specific active suicidal thoughts.

CRS-BS-TP-000005 V 1.0

Page 100 of 127

Cytel Confidential: This is a controlled document and shall not be changed, saved, copied or reproduced by any unauthorized

Sponsor:	ObsEva			
Protocol:	18-OBE2109-00	18-OBE2109-003		
Document Version No.:	V5.0	Document Date:	13-JUN-2022	

- 3. Active suicidal ideation with any methods (not plan) without intent to act.
- 4. Active suicidal ideation with some intent to act, without specific plan.
- 5. Active suicidal ideation with specific plan and intent.

If data of suicidal ideation or behavior is missing at baseline then the subject will not be included in summaries of emergence or worsening of suicidal ideation or behavior. The "already enrolled subjects" C-SSRS version ("Prior to Entry Study") will be used as baseline for subjects already randomized at the time of implementation of Amendment 3. If a subject completed this "prior to Entry Study" questionnaire at several visits, the worst severity answers will be considered as baseline in the analysis.

The same analysis will be repeated at any time post-baseline from Month 1 FU to Month 6 FU, on the follow-up Safety analysis set.

4.8.11. Time to the first post-treatment menses

The first post-treatment menses will be defined from the Vaginal Bleeding daily ediary, as the first day for which the subject recorded bleeding after the last treatment administration date of the main study, i.e., the first day with "BLEEDING" or "HEAVY BLEEDING" after the last treatment administration date of the main study.

Time to first post-treatment menses is defined as:

Time to first post-treatment menses (days) = (day of first post-treatment menses - last treatment administration date) + 1

Only data from the follow-up treatment period will be included, and the analysis will be provided on the Follow-up Safety Analysis Set, by treatment group.

Subjects who have not recorded any bleeding up to the end of the follow-up period will be considered as right-censored data at the last ediary vaginal bleeding record date before the end of the main follow-up period (as defined in section 4.2.11) with time of censoring = last non-missing ediary vaginal bleeding record date – last treatment administration date +1.

The probability of subjects having bleeding will be displayed by treatment group in the form of cumulative probability curves estimated using the non-parametric Kaplan-Meier method. Point estimates and corresponding 2-sided 95% CIs using the Greenwood's variance estimate will be provided at 28 days, 56 days, 84 days, 112 days, 140 days, 168 days, 196 days after the last treatment administration date. Percentiles (25th, 50th, and 75th) and corresponding 2-sided 95% CIs will also be provided; "N/A" will be presented for any of the percentiles not reached.

Subjects with or without first post-treatment menses, time to first post-treatment menses, end of study status and end of study date will be presented in a by-subject listing.

Sponsor:	ObsEva		
Protocol:	18-OBE2109-003		
Document Version No.:	V5.0	Document Date:	13-JUN-2022

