10.2.2.5 Study visit: Month 6 (day 169 ± 3 days)

The following tests and evaluations will be performed :

- eDiary completion compliance check
- ePRO and ClinRO completion, ideally before any other procedures or assessments: EHP-30, HRPQ, HRUQ, PSIQ, SSIQ, PROMIS, EQ-5D-5L, specific monthly severity questions, mPGIS, PGIC completion (anchors must be completed last)
- Concomitant treatments recording
- AE recording
- Completion of the paper C-SSRS questionnaire (version for “already enrolled subjects” (see Appendix S) for patients responding to the C-SSRS for the first time during the study, or version “since last study visit” (see Appendix T) for patients for whom the C-SSRS was completed at the previous study visit)
- Final IMP accountability based on blisters
- ECG (at about the same time as but before the PK sample)
- Physical examination, including weight recording
- Vital signs (BP and heart rate)
- Urine pregnancy test
- Gynecological examination
- Manual breast examination (by palpation)
- TVUS of uterus
- Urinary protein dipstick
- Fasting (overnight) blood samples for haematology, coagulation parameters, chemistry, lipids, hormones and bone biomarkers

- Pre-dose PK samples (the time of dose administration on previous 4 days and time of PK sampling will be recorded)
- Endometrial biopsy, unless the endometrium thickness in TVUS is ≤ 5 mm, in which case no endometrial biopsy will be necessary (see section 10.4.5). Appropriate photo documentation of the endometrium thickness is mandatory.
- BMD assessed by DXA for femoral neck, hip and spine. DXA can be performed up to 10 days prior to the study visit which allows to get the DXA results ideally at the time of the Month 6 study visit at the latest, knowing that subjects who experience more than 8% BMD loss or a Z-score ≤ -2.5 will not be eligible to enter the extension study.
- The subject will be verbally asked which treatment she believed she received during the blinded Treatment Period. The answer will be recorded in the eCRF.
- Contraception dispensing (if applicable) and counselling

An additional question will be asked to the subject about the burden of filling in the eDiary (0 = not at all a burden, 10 = very much a burden). The answer will be recorded in the eCRF.

Study visit Month 6 constitutes the end of the Treatment Period.

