11.2 DOSAGE AND ADMINISTRATION

Linzagolix and corresponding placebo treatments will be supplied as film-coated tablets for oral administration and given as monthly treatment kits (Figure 5).

ABT and corresponding placebo will be supplied as red capsules and given as 3-monthly treatment kits.

IMP treatment will start on Day 1 and will be administered once daily up to the day preceding the Month 6 visit. The subjects will have to swallow two tablets of linzagolix/placebo and one capsule of ABT/placebo, ideally at the same time each day.

On the day of a study visit, the subject must take the study medication at site, after the PK blood sample collection, except on Day 1 visit where the study medication must be taken before the PK blood sample collection (at least 1.5 h before). The site staff will record in the eCRF the time of study medication intake. The linzagolix/placebo tablets must be taken from the kits dispensed on that visit (and not from the previously dispensed kits). On Day 1 and Month 3 visits, ABT/placebo capsules must be taken from the kits dispensed during these visits. On Month 1, 2, 4 and 5 visits, ABT/placebo capsules must be taken from the previously dispensed kits.

The treatment groups are described below:

Treatment group	Daily dose Day 1 to Month 6			
	Linzagolix active tablets	Linzagolix placebo tablets	ABT active capsules	ABT placebo capsules
75 mg	1 □ 75 mg	1 □ placebo 200 mg	None	1 capsule
200 mg	1 □ 200 mg	1 □ placebo 75 mg	1 capsule	None
Placebo	None	1 □ placebo 75 mg AND 1 □ placebo 200 mg	None	1 capsule

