4.2.11. Last treatment administration date, End of Study date and Period definitions

The last treatment administration date will be defined as the date from the treatment termination of main period eCRF page. If this date is missing, the last date with a drug intake in eDiary strictly inferior to Month 6 date or the last date with a drug intake in eDiary available if the subject discontinued will be used.

For each 28-day period prior to Month X (except Month 6), the end of the period will be defined as the Month X visit date. If subject discontinued prior to Month X, the end of the period will be the date from the treatment termination of main period eCRF page or the last date with a drug intake in the eDiary if missing. If the subject missed the Month X visit (but did not discontinued), the subject might still have filled the diary during that time: the theoretical Month X date will be used to define the end of the 28-day period. The theoretical Month X is defined with respect to Day 1 as Month X= Day 1+ 28*X. Theoretical visits are presented in Table 3 of Section 4.2.9.

For the 28-day period prior to Month 6, the end of the period will be defined as the last treatment administration date.

The end of study date will be Month 6 date -1 day for subjects entering the Extension, and the last assessment date defined as last eCRF (excluding AE and CM end dates) or eDiary date in main study or main Follow-up for subjects not entering the Extension. This will not necessarily be the same date as last assessment date as recorded in the eCRF.

Note: For summaries by visit (efficacy or safety), the Month 6 assessments will be included in the main study analyses. For Adverse Events, Concomitant Medications and Daily diaries, data collected on Month 6 date will be part of the extension for subjects entering the extension study, and be part of the Follow-up period for subjects entering the main study follow-up period.

The main treatment period will be defined as Day 1 up to (Month 6 date -1) or treatment discontinuation date.

The main follow-up period will be defined as the Month 6 date or (treatment discontinuation date+1) up to the end of study date (for subjects who entered the follow-up).

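### SAP 4.8.11 takes the first BLEEDING or HEAVY BLEEDING day after the last dose as first post-treatment menses without requiring a new onset, so a bleed already under way is scored as recovery at 2 days

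*SAP*

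**What the plan says.** Time to first post-treatment menses is a named safety endpoint (Protocol 7.2, SAP 2.5.3). SAP 4.8.11 defines the event from the daily bleeding diary as "the first day with 'BLEEDING' or 'HEAVY BLEEDING' after the last treatment administration date of the main study" and the time as "Time to first post-treatment menses (days) = (day of first post-treatment menses - last treatment administration date) + 1". Spotting is a separate diary grade (Protocol 10.3.2.3) and is not an event.

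The analysis is restricted: "Only data from the follow-up treatment period will be included, and the analysis will be provided on the Follow-up Safety Analysis Set". SAP 4.2.11 sets the window: "The main follow-up period will be defined as the Month 6 date or (treatment discontinuation date+1) up to the end of study date". Diary data from the Month 6 day itself will "be part of the Follow-up period for subjects entering the main study follow-up period". Protocol 11.2 fixes the last planned dose: "IMP treatment will start on Day 1 and will be administered once daily up to the day preceding the Month 6 visit". SAP section 5 confirms that women going into follow-up take no dose on the Month 6 day.

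The Month 6 visit includes this procedure: "Endometrial biopsy, unless the endometrium thickness in TVUS is ≤ 5 mm, in which case no endometrial biopsy will be necessary". Women who stop between Month 3 and Month 6 undergo the Month 6 procedures (Protocol 10.7.2). Women without a Month 6 biopsy are to have one during follow-up, from Month 1 FU onwards (Protocol 10.2.3 and 10.4.5).

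Results are Kaplan-Meier curves by arm, point estimates every 28 days from 28 to 196 days, quartiles, and a by-subject listing. No test is planned.

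**The concern.** The endpoint is meant to describe how soon menses return once treatment stops. The rule measures something else: the first pad-requiring bleeding day after the last dose, whatever its origin. It sets no bleed-free interval and no exclusion for a procedure. Two kinds of bleeding that are not a return of menses therefore qualify: a bleed that started on treatment, and procedural bleeding after a biopsy.

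The diary offers no other way to separate them. The questions identifying the first day of a period are described for the screening period only (Protocol 10.3.2.3). The mapping rules in SAP Appendix E delete answers to them that were collected in error after Day 1.

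The protocol treats failure to resume menses as worth acting on: Protocol 10.2.3.3 calls for an FSH test and advice to seek a gynaecological evaluation in women without menses by Month 3 FU. A rule that converts some of these women into day-2 events hides the cases that the endpoint should show.

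**Working it through.** The documents state no figure for this endpoint, so there is none to reproduce. The steps below apply the SAP formula directly.

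**Step 1: earliest possible event.** Call the last dose date day 0. For completers the Month 6 visit is day 1, and it is inside the follow-up window. Bleeding on that day scores 1 − 0 + 1 = 2 days. SAP 2.5.2 lists Month 6 among the visits with a dose at site, which conflicts with Protocol 11.2 and SAP section 5. If a dose were taken that day, the first eligible day would move to the next day and would still score 2. For early discontinuers the window opens on the discontinuation date + 1, with the same result.

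**Step 2: carried-over bleeding.** A woman bleeding on day 0 and day 1 has her event at 2 days. If she has no menses for the rest of follow-up, she is still an event at 2 days and can be neither delayed nor censored.

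**Step 3: size among women still cycling.** Inputs:
- Cycle length C. Inclusion criterion 8 allows 42 to 76 days over two cycles, so a mean of 42/2 = 21 to 76/2 = 38 days. I use 28, with 21 and 38 as the range.
- Pad-requiring days B. Not in the documents; assumed 5, range 3 to 7.
- Cycle day on day 1. Assumed uniform over 1 to C.

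Share carried over from treatment = (B − 1)/C = 4/28 = 14.3% (range 2/38 = 5.3% to 6/21 = 28.6%). Share scored at 2 days under the SAP = B/C = 5/28 = 17.9%. Under a new-onset rule it is 1/C = 1/28 = 3.6%.

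For C = 28 and B = 5, the 28 equally likely starting days give these times:
- SAP rule: five values of 2, then 3 to 25.
- New-onset rule: 2 to 29, one each. The four carried-over women move from 2 days to 26–29 days.

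| | SAP rule | New onset |
|---|---|---|
| Scored at 2 days | 17.9% | 3.6% |
| 25th percentile | 4.8 | 8.8 |
| Median | 11.5 | 15.5 |
| Event by 28 days | 28/28 = 100% | 27/28 = 96.4% |

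Over the nine combinations of C (21, 28, 38) and B (3, 5, 7), the median moves later by 2 to 6 days. The 28-day proportion is unchanged at C = 21. At C = 38 and B = 5 it falls from 81.6% to 71.1%. The latest new-onset time at C = 38 is 39 days, so every such woman has an event before 56 days under either rule.

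**Step 4: direction.** A new-onset day is also a bleeding day after the last dose, so its date equals the SAP date or falls later. The error cannot run the other way.

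**Step 5: biopsy.** BLEEDING-grade loss on the day of a Month 6 biopsy scores 2 days, and loss one to three days later scores 3 to 5 days. For a completer with last dose on Day 168, a Month 1 FU biopsy at Day 197 ± 7 falls at 190 − 168 + 1 = 23 to 204 − 168 + 1 = 37 days, around the 28-day estimate. The documents give no rate of post-biopsy bleeding at that grade, so no size can be attached.

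**The case against.** The strongest case on the other side is that the effect is small and confined. The analysis is descriptive, has no test and no place in the multiplicity scheme, and covers only women who entered drug-free follow-up. The listing shows each woman's time, so day-2 events can be seen. For women still cycling, everything from 56 days on is unaffected. The worked figures also describe women with regular cycles, for whom recovery from suppression is hardly the question. All of this stands, and it sets the severity.

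Spotting does not count, which filters out some light procedural loss. That stands too: the point concerns days graded BLEEDING or HEAVY BLEEDING, not any bleeding.

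A reader might infer that the arms are not comparable, since on-treatment bleeding and endometrial thickness (hence biopsy timing) could differ by treatment. The documents give neither the active-arm share of carried-over bleeding nor a biopsy bleeding rate. A difference between arms is possible but not shown.

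A poorly chosen remedy would also overshoot. If both bleed-free look-back days had to fall after the last dose, the earliest event time would be 4 days. Genuine onsets on the first two post-treatment days (2/28 = 7.1%) would then be discarded until the next cycle. At C = 28 and B = 5 the times become 4 to 31, the median 17.5 days, and the 28-day proportion 25/28 = 89.3%. At 28 days that is 7.1 points from the new-onset value, against 3.6 points for the SAP rule. The look-back must therefore be allowed to reach into treatment.

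**Conclusion.** The definition gives a wrong event date for any woman whose bleed continues past the last dose, and nothing elsewhere in the plan corrects it. Severity is minor. Under the assumed 28-day cycle with 5 pad-requiring days and a uniform cycle day, 14% of women still cycling are affected, with the effect falling on the quartiles and, for cycles of about 28 days or longer, the 28-day estimate. The consequence that matters most for interpretation is the woman with a carried-over bleed and no later menses, who appears as recovered at day 2. How many such women there are in each arm, and how much biopsy bleeding adds, cannot be derived from the documents. Type I error and power are untouched.

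**What to change.** In SAP 4.8.11, define the event as the first BLEEDING or HEAVY BLEEDING day after the last dose that starts a new episode: one preceded by at least 2 consecutive recorded diary days without BLEEDING or HEAVY BLEEDING. State that these look-back days may be on-treatment days and that spotting does not break the interval. Word the censoring sentence to match. Keep the current definition as a second line in the table. Add a sensitivity analysis that ignores bleeding starting within 3 days after any biopsy, at Month 6 or in follow-up.

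The cost is SAP wording and programming; the daily diary and biopsy data are already collected. The drawback is that missing diary days just before an onset can delay an event by one episode, which the second line in the table will make visible.

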7.2 SAFETY ENDPOINTS

- Change from baseline to each scheduled assessment in BMD measured by DXA of lumbar spine (L1-L4), femoral neck, and total hip
- Incidence and severity of treatment emergent adverse events (TEAEs)
- Incidence and severity of hypoestrogenic TEAEs (hot flush)
- Time to the first post-treatment menses
- Changes in clinical laboratory assessments (hematology, biochemistry, coagulation parameters, hormones, lipids and urinalysis) from baseline to each scheduled assessment
- Any pathological changes from baseline in the endometrium as assessed by histology from endometrial biopsies

- Changes from baseline to each scheduled assessment in any other safety parameter including weight, vital signs, ECG, gynecological assessments and endometrial thickness

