9 STUDY POPULATION

9.1 SUBJECTS

9.1.1 Description of the target population

The target population will be premenopausal women aged 18 to 49 years inclusive at screening, with surgically and, if available, histologically confirmed pelvic endometriosis and with moderate to severe EAP.

They must not be planning to become pregnant and must agree to use double non-hormonal barrier contraception from screening until 3 months after the end of treatment. From 3 months after the end of treatment to the end of the drug-free follow-up period, contraception is still mandatory but hormonal contraception is allowed.

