10.6.2 Prohibited Medicines

Medication listed in exclusion criteria (see section 9.2.2) will be prohibited up to Month 6.

To consider a subject who is currently taking any prohibited therapies for potential inclusion in this study, the Investigator must ensure that the subject has sufficient washout time prior to screening (see Section 10.2.1).

Strong CYP3A4 inhibitors or inducers are prohibited up to end of treatment in view of the ABT (Appendix P).

Linzagolix is considered to be a weak inhibitor of CYP2C8. Substrates to CYP2C8 with a narrow therapeutic index should be administered with caution.

Hormonal contraception including hormonal IUD must be stopped following ICF signature until 3 months after end of treatment.

When a prohibited medication or treatment is necessary for the subject's well-being, the sponsor must be notified and possible alternatives are to be discussed before administration of the prohibited medication or treatment whenever possible.

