10.6.3 Non-Drug Therapies

Contraceptive use:

For subjects of childbearing potential and requiring contraception, non-hormonal contraception is required from beginning of screening period until 3 months after the end of treatment. Two forms of non-hormonal contraception will be required e.g. condom with spermicide (if in the opinion of the investigator a woman is at risk of acquiring HIV, spermicide should be avoided; condom with diaphragm may be used). Suitable condoms with spermicide will be provided free of charge to subjects over the duration of the study.

After 3 months after the end of the Treatment Period until the end of the Follow-up Period, contraception is still required but hormonal contraception is allowed.

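### Time to first post-treatment menses ignores hormones started in follow-up: after about Day 84 a withdrawal bleed counts as return of menses and hormone-induced amenorrhoea counts as event-free time at risk

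*SAP*

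**What the plan says.** Protocol 7.2 lists "Time to the first post-treatment menses" among the safety endpoints. SAP 4.8.11 defines the event from the daily diary as "the first day for which the subject recorded bleeding after the last treatment administration date of the main study", limited to the two heavier categories, so spotting alone is not an event. No condition is placed on the cause of the bleed.

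The only censoring rule, which dates censoring to the final bleeding entry in the diary before follow-up ends, is: "Subjects who have not recorded any bleeding up to the end of the follow-up period will be considered as right-censored data at the last ediary". SAP 4.2.11 sets that end: "The main follow-up period will be defined as the Month 6 date or (treatment discontinuation date+1) up to the end of study date". The analysis is Kaplan-Meier by treatment group on the Follow-up Safety Set, with estimates at 28, 56, 84, 112, 140, 168 and 196 days and three percentiles. The by-subject listing shows menses status, time, and end-of-study status and date, but not hormone use.

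On hormones, Protocol 10.6.2 bars hormonal contraception until three months after treatment. After that, Protocol 10.6.3 says that "until the end of the Follow-up Period, contraception is still required but hormonal contraception is allowed". For the other exclusion-list medicines, which include GnRH analogues, danazol and sex hormones, Protocol 10.6.2 says: "Medication listed in exclusion criteria (see section 9.2.2) will be prohibited up to Month 6". Protocol 10.6 has concomitant medication recorded in the eCRF for the whole study. SAP 4.8.7 defines concomitant medication only up to the last dose.

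**The concern.** The endpoint is there to describe how quickly menses return once study drug stops. From about Day 84, contraception is required and hormonal methods are permitted, in women with endometriosis pain who have come off treatment. Protocol 5.3 itself describes combined oral contraceptives as a frequent initial therapy and abolition of menstruation as an aim of hormonal treatment. Hormone use in this window is therefore foreseeable.

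Once a woman starts hormones, her diary reflects the hormone as well as her own recovery. The stated rule does not separate the two. The women affected are those of most safety interest: Protocol 10.2.3.3 calls for an FSH test and advises a gynaecological evaluation for those without menses at Month 3 of follow-up. If return is slower in one arm, more of that arm is exposed, so the comparison between arms can be affected as well as the level.

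**Working it through.** **Plan's own figure.** None exists. The documents give no return rate, hormone uptake or event count for this endpoint.

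**Tracing the rule.** Take two women without menses at Day 84 who start hormones then.
- One has a withdrawal bleed recorded as bleeding. SAP 4.8.11 counts an event on that day.
- One is kept amenorrhoeic. She has no event and stays in the risk set until her last diary record, which lowers the estimated cumulative return.

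No section of the SAP censors, excludes or runs a sensitivity analysis for either.

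**Which time points are exposed.** A month is 28 days, so the contraception bar ends at 3 × 28 = 84 days. The diary is collected at Month 6 FU, Day 337 ± 7 from Day 1. The last dose is the day before the Month 6 visit (Day 169 ± 3), so at the earliest Day 165. The longest on-schedule time is 344 − 165 + 1 = 180 days. For early stoppers it is 168 + 7 + 1 = 176 days. Day 196 therefore lies beyond scheduled observation, and the exposed estimates are Days 112, 140 and 168.

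**Illustration at Day 168 (all inputs assumed).** Let F = share with menses by Day 84, r = share of the rest who would return naturally by Day 168, and u = share of the rest who start hormones at Day 84 for reasons unrelated to prognosis. Expected Kaplan-Meier cumulative return:
- censored at hormone start: F + (1 − F)r
- as written, every user has a withdrawal bleed: F + (1 − F)[(1 − u)r + u]
- as written, every user suppressed: F + (1 − F)(1 − u)r

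With r = 0.5:

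| F | u | Censored at start | All withdrawal bleeds | All suppressed |
|---|---|---|---|---|
| 70% | 50% | 85.0% | 92.5% | 77.5% |
| 80% | 30% | 90.0% | 93.0% | 87.0% |
| 90% | 30% | 95.0% | 96.5% | 93.5% |
| 95% | 10% | 97.5% | 97.75% | 97.25% |

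Over F = 70% to 95% and u = 10% to 50%, the shift runs from about 0.3 to 7.5 points in either direction.

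**Mixed use.** If a share w of users has a withdrawal bleed and the rest are suppressed, the shift is (1 − F)·u·(w − r). Its sign depends on w and r, neither of which the documents give. At w = r it is zero.

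**Second illustration, Day 140 (also assumed).** Suppose 10% have no menses at Day 84, natural return is then exponential with mean 100 days, and half start hormones on Days 85 to 98.
- Non-return without hormones: 0.10 × exp(−56/100) = 5.7%.
- As written, all cyclic with a bleed 21 to 28 days after start: only non-users remain, 0.05 × 0.571 = 2.9%.
- As written, all suppressive: 2.9% plus users with no natural bleed before starting, 0.05 × about 0.93 = 4.6%, total 7.5%.

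**The case against.** **The shift may be smaller than the sampling error.** In the 80%/30% row it is 3.0 points. With all 150 planned women of an arm in follow-up, the 95% half-width at 90% is 1.96 × √(0.9 × 0.1/150) = 4.8 points; with an assumed 50 per arm it is 8.3. The Follow-up Safety Set omits women who enter the extension, so it will be smaller than 150. This stands as a limit on importance, but a wide interval does not remove a bias. A reader might infer that the tail is driven by which hormone was started. With every input assumed, that is not shown.

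**Hormone use may be uncommon.** Women with tubal ligation, a vasectomised partner or habitual abstinence have less reason to start hormonal contraception. Exclusion criterion 7 also removes women likely to need sex hormones or GnRH analogues during the study. Both points limit the size and leave the rule unchanged.

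**Suppressed women are not labelled as failures.** A reader might infer that they are scored as not recovered. They are not: they are right-censored at the last diary record, too late rather than wrongly classified. The time on hormones still lowers the curve.

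**Censoring at hormone start may itself be biased.** A reader might infer from the working that it recovers the true value. It does so there only because hormone start was assumed unrelated to prognosis. Women referred for evaluation, or whose pain returns, may start for reasons tied to ovarian recovery. This objection stands, and the fix allows for it.

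**The information may be partly visible.** SAP 4.8.7 promises a by-subject medication listing, and the date rules in SAP 4.2.8.2 recognise post-treatment medication. A careful reader might match the listings by hand, but the reported estimates would not change.

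**Conclusion.** The gap is real and moderate: it should be closed, but it does not threaten the trial's main conclusions. The endpoint is descriptive, with no test attached, so neither type I error nor power is involved.

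The effect is confined to women without menses by about Day 84 who then start hormones. It reaches mainly the Day 112, 140 and 168 estimates and any percentile after Day 84. A median reached before Day 84 would not move. That boundary assumes the contraception rule is followed and that no other hormone is started earlier. Protocol 10.6.2, read literally, does not extend the bar on the other listed medicines past Month 6.

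Size and net direction cannot be stated. The 0.3 to 7.5 points is a range under assumptions, and mixed hormone use would partly cancel. A reader might infer that the plan over- or understates recovery; the documents support neither.

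**What to change.** Add to SAP 4.8.11 an analysis in which a woman who begins any sex hormone, hormonal contraceptive, hormonal IUD or GnRH analogue after the last dose and before first menses is censored at the start date in the eCRF. Present it beside the analysis under the current rule. Report the number so censored by arm, and add hormone type and start date to the by-subject menses listing. State how partial start dates are handled, because SAP 4.2.8.2 limits its imputation to assigning the treatment period.

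Because hormone start may be related to ovarian recovery or returning pain, a version treating it as a competing event is a reasonable companion.

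Protocol 13.6.3 unblinds the sponsor after Month 6, so the change should be dated and labelled as added. SAP V5.0 already added follow-up-only sensitivity analyses, and SAP 4.3 foresees a second presentation of results after Month 6 FU.

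The cost is a short SAP addition and one more table; no new data are needed. The statistical cost is fewer women at risk and wider intervals after Day 84, with possibly informative censoring.
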